1.0 Objectives

1.1 Describe the purpose, specific aims, or objectives of this research.

Response:

The purpose of this project is to develop and test affordable, effective strategies to reduce caregiver burden and associated negative effects (e.g., depression and fatigue) and to increase caregivers' satisfaction and self-efficacy, so that they can continue providing home-based care to their care recipients (CRs) who are members of the Program of All-inclusive Care for the Elderly (PACE). This project will connect PACE organizations and university occupational therapy (OT) graduate level curriculum to produce a practical, sustainable care model. In this project, a research component pertains to assess effectiveness of OT interventions

1.2 State the hypotheses to be tested, if applicable.

NOTE: A hypothesis is a specific, testable prediction about what you expect to happen in your study that corresponds with your above listed objectives.

Response:

We have three reteach questions and two hypotheses.

1. What are challenges that caregivers are facing in caring for their care recipients?
2. Which solutions were accepted and effective?
3. The intervention group will reduce caregiver burden and depression, while the control group will not.
4. The intervention group will increase the scores of positive aspect of caregiving and self-efficacy while the control group will not.
5. At 6-months after intervention, does the effect of our intervention exist?

In addition, we will identify the rate of care recipients who live in the community opposed to moving to a nursing home for both groups, and the number of falls and emerveny visits of care recipients.

Scientific Endpoints

2.1 Describe the scientific endpoint(s), the main result or occurrence under study.

*NOTE: Scientific endpoints are outcomes defined before the study begins to determine whether the objectives of the study have been met and to draw conclusions from the data. Include primary and secondary endpoints. Some example endpoints are: reduction of symptoms, improvement in quality of life, or survival. Your response should **not** be a date.*

Response:

Primary endpoint for the study is the reduction of caregiver burden and depression. Secondary endpoints is the improvement in positive aspect of caregiving and self-esteem.

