addressing the medical needs of the care recipient rather than the caregiver. Another finding from previous research is that interventions that are individually customized to the care recipient and caregiver's needs are more effective than generalized interventions (Pinquart & Sørensen, 2006). There are interventions and educational programs for caregivers that have shown to be effective (Austrom & Lu, 2009). Support groups are effective to help caregivers, but currently no program supports caregivers by instructing how to provide care for care recipient's ADLs, which is the core of caregiving tasks. Occupational therapist (OT) can apply their knowledge in providing care for patients with dementia to caregivers. In doing so, we realize that practical solutions for the challenges that caregivers are facing can be developed using a caregiver-centered approach, rather than a top-down approach. Therefore, individualized interventions for the caregiver determined on a case-by-case basis by a team of gerontologists, occupational therapists, and occupational therapy students, which can be finalized by the input from caregivers, may lead to a better outcome for caregiving situations. In addition we explore if positive effects of caregiver support will last six months after the intervention because it will find if continuous support is needed for this target population. Currently, related studies do not exist.

2.2 Include complete citations or references.

2.3

Response:

Austrom M G, & Lu, Y. (2009). Long term caregiving: helping families of persons with mild cognitive impairment cope. *Current Alzheimer Research*, 6 (4), 392-398.

Dean K & Wilcock G. (2012) living with mild cognitive impairment: the patient's and carer's experience. *International Psychogeriatrics*, 24(6), 871-881.

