3.0 Study Design

3.1 Describe and explain the study design (e.g. case-control, cross-sectional, ethnographic, experimental, interventional, longitudinal, observational).

Response:

We will use a qualitative method to understand difficulties that caregivers are facing and to document solutions and their implementation process; and a quantitative method using a randomized contoured trial with pre-, post- and follow-up experimental design. A treatment group will receive a 1 to 2-month interventions to solve caregiving challenges, and a control group will receive usual support. Assessments will be conducted at baseline, 2 months (posttest), 4 months (follow-up), and 6 months post intervention.

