10.0 Study Timelines

10.1 Describe the anticipated duration needed to enroll all study subjects.

Response:

The duration need to enroll all participants is 19 months.

10.2 Describe the duration of an individual subject's participation in the study. Include length of study visits, and overall study follow-up time.

Response:

Each participant intervention is 1-2 months and it will take 30 – 45 minutes for each of 4 time assessments. From the beginning of the contact to the end of 4h assessments, it will be about 10 months.

10.3 Describe the estimated duration for the investigators to complete this study (i.e. all data is collected and all analyses have been completed).

Response:

2. 5 years

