16.0 Data Management and Analysis

16.1 *Describe the data analysis plan, including any statistical procedures. This section applies to both quantitative and qualitative analysis.*

Response:

For two hypotheses, we first analyze a linear trend of dependent variables over time. If they are linear, we will use Generalized Estimating Equation to compare the two groups' slopes. A main effect and an interaction effect will be examined. If it is not, we will use Repeated Measures ANOVA with a between-factor. The contrasts within a group and the difference between groups will be performed as post hoc tests. To answer the last research question to find the difference between

the 4-months data and 6 month after intervention (or at 10 months), we will use Repaeated measurs ANVA with a between-factor.

To answer research questions, we will list all challenges for both groups and solutions for the treatment group. The effectiveness of solutions will be evaluated using a Likert Scale (from very effective to not effective at all) and percentages will be reported. For the rate of continued community, living at 4 months will be tabulated for both groups and a chi-square test will be used. The number of falls and emergency visits will be compared for these two groups using Mann Whitney U-test.

The significance level for primary analyses will be set at .05. SPSS 26.0 will be used for statistical analyses.

16.2 If applicable, provide a power analysis.

NOTE: This may not apply to certain types of studies, including chart/records reviews, survey studies, or observational studies. This question is asked to elicit whether the investigator has an adequate sample size to achieve the study objectives and justify a conclusion.

Response:

The sample size for this study was determined by a power analysis based on the study similar to our study (Kamiya et al., 2014). The effect size found in the article was $d = .65$. We will use a directional hypothesis; therefore, we set $\alpha = .05$, and in order to achieve 80% of statistical power, we will need 30 participants in each group, therefore 60 in total. Expecting 25% of attrition, we will recruit 75 participants.

16.3 Describe any procedures that will be used for quality control of collected data.

Response:

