17.0 Provisions to Monitor the Data to Ensure the Safety of Subjects

- N/A: This study is not enrolling subjects, or is limited to records review procedures only. This section does not apply.

NOTE: *Minimal risk studies may be required to monitor subject safety if the research procedures include procedures that present unique risks to subjects that require monitoring. Some examples include: exercising to exertion, or instruments that elicit suicidality or substance abuse behavior. In such cases, N/A is not an acceptable response.*

17.1 Describe the plan to periodically evaluate the data collected regarding both harms and benefits to determine whether subjects remain safe.

Response:

We will not periodically evaluate the data collected but we will collect data every 2 months for three times. The study will identify depression. If the total score of CES-D is 15 or higher at the time of interview, this will be reported to the participant and the PACE for an appropriate intervention.

17.2 Describe what data are reviewed, including safety data, untoward events, and efficacy data.

Response:

The total score of the Center for Epidemiology Study-Depression will be used to detect depression, which is a considered mental illness.

17.3 Describe any safety endpoints.

Response:

The CES-D total score of 14 or less (not depressive) and 15 or higher (indicative of depressive symptom). One of the purpose of the study is to decrease the CES-D score.

17.4 Describe how the safety information will be collected (e.g., with case report forms, at study visits, by telephone calls with participants).

Response:

Face-to face interviews.

17.5 Describe the frequency of safety data collection.

Response:

Three times in 4 months.

17.6 Describe who will review the safety data.

Response:

Study OTGS and the PI

17.7 Describe the frequency or periodicity of review of cumulative safety data.

Response:

We do not have cumulative safety data. When each time we interview participants, we will review the data.

17.8 Describe the statistical tests for analyzing the safety data to determine whether harm is occurring.

Response:

The sum of 20 item CES-D scores will be used.

17.9 Describe any conditions that trigger an immediate suspension of the research.

Response:

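### The final assessment has two dates that do not agree: six months after a 1-2 month intervention (month 7-8) and about month 10.

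*Combined protocol and SAP*

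**What the plan says.** **Length of the intervention.** Section 3.1 states "A treatment group will receive a 1 to 2-month interventions to solve caregiving challenges", and section 10.2 repeats it: "Each participant intervention is 1-2 months". The control group receives usual support.

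**Assessment schedule.** Section 3.1: "Assessments will be conducted at baseline, 2 months (posttest), 4 months (follow-up), and 6 months post intervention". Section 17.1 confirms the spacing of the first three: "we will collect data every 2 months for three times".

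**Final assessment tied to the intervention.** Question 5 in section 1.2 asks: "At 6-months after intervention, does the effect of our intervention exist". Background 2.1 gives the reason: "we explore if positive effects of caregiver support will last six months after the intervention because it will find if continuous support is needed". Section 9.1 schedules the final telephone call six months after the intervention.

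**Final assessment tied to about month 10.** Section 10.2 gives the length of participation: "From the beginning of the contact to the end of 4h assessments, it will be about 10 months". In section 9.1, the same final call asks about the care recipient's falls and emergency visits over the preceding 10 months.

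**Both at once.** Section 16.1 sets the comparison for the last research question as the difference between "the 4-months data and 6 month after intervention (or at 10 months"), using repeated-measures ANOVA with a between-subjects factor.

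**The concern.** The last assessment is the only one that bears on durability, and its date depends on which sentence is followed. Staff reading the procedure in section 9.1 would telephone about six months after a caregiver's intervention ended. Staff reading section 10.2 would telephone at about month 10. The control group has no intervention to end, so a date defined by the end of the intervention gives that arm no clock at all.

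The date affects two results. The first is question 5, which Background 2.1 intends to use to decide whether support must be continuous. If the call is at month 10 but is reported as six months, a faded or absent group difference could be read as an effect that did not last six months, when no assessment was made at that point. A group difference that persists would not mislead in this way, since it would still show an effect beyond six months. The second is the Mann-Whitney comparison of falls and emergency visits, which needs a recall period that is the same in both arms and does not include time before the study began.

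A related gap is that the only comparison named for question 5, month 4 against the final assessment, does not directly estimate what the question asks.

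**Working it through.** **Inputs.** Intervention length 1-2 months (3.1, 10.2). First three assessments at months 0, 2 and 4 (3.1, 17.1). Final assessment six months after the intervention (1.2, 2.1, 3.1, 9.1, 16.1) and also about month 10 (10.2, 16.1, and by implication the 9.1 recall window). The intervention is first taken to start at baseline.

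**Step 1: can the equation in 16.1 be reproduced?** Final month = anchor + 6.

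| Anchor for the six months | Final month |
|---|---|
| Intervention ends at month 1 | 1 + 6 = 7 |
| Intervention ends at month 2, or posttest at month 2 | 2 + 6 = 8 |
| Posttest read from 9.1 as one month plus two | 3 + 6 = 9 |
| 4-month follow-up | 4 + 6 = 10 |

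Only the 4-month follow-up gives month 10. No section says that the six months run from there.

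**Step 2: if the call is at month 10.** Time since the end of the intervention is 10 − 2 = 8 to 10 − 1 = 9 months. Against the stated six, that is 8 − 6 = 2 to 9 − 6 = 3 months longer. If the intervention starts a week after baseline (9.1 has solutions presented within a week), the interval becomes 10 − 2 − 7/30.4 = 7.8 to 10 − 1 − 7/30.4 = 8.8 months.

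**Step 3: if the call is at month 7-8.** A 10-month recall starts 10 − 8 = 2 to 10 − 7 = 3 months before baseline. Between 2/10 = 20% and 3/10 = 30% of the recalled period would then precede the study.

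**Step 4: what the named comparison tests.** Write D4 and DF for the between-group differences at month 4 and at the final assessment. In a repeated-measures ANOVA on those two times:

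- the group-by-time term tests DF − D4;
- the group term tests the average (D4 + DF)/2;
- question 5 asks about DF.

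DF − D4 = 0 both when an effect is fully maintained (D4 = DF, not zero) and when it had already gone by month 4 (D4 = DF = 0). The interaction cannot tell these apart, and the group term mixes the final difference with the month-4 one.

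**The case against.** The strongest reply is that the authors may count the whole contact phase as the intervention. Section 9.1 mentions 4-6 home visits directly after describing the 4-month interview, and section 23.4 describes telephone contacts about whether solutions are working. If the intervention ran to month 4, then 4 + 6 = 10 and the labels agree. This is a plausible explanation of how the wording arose, but it is inference. It conflicts with the 1-2 months given in 3.1 and 10.2, and with 3.1 calling month 2 the posttest and month 4 the follow-up. If it is what was meant, those sections need correcting instead.

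A second reply is that 8-9 months is too exact. This stands in part. Section 10.2 says about 10 months and counts from first contact, which comes before the baseline visit by an interval that the documents do not give. That shortens the gap somewhat, as does a start a week after baseline. The figures are approximate.

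Third, a null on the month-4 versus final change would suggest that the effect was maintained, and 16.1 does print the 10-month label. Both are true. The risk of misreading therefore lies in a reduced or absent group difference that is reported under the six-month label.

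Fourth, 16.1 already allows post hoc contrasts between groups. It places them under the two hypotheses, and does not name a contrast at the final assessment as the answer to question 5.

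A reader might infer more: that the call will certainly be made at month 10, so that question 5 is bound to report the wrong interval. The documents do not support that. Section 9.1 is the operational text, and followed literally it puts the call at month 7-8. Question 5 would then have the right interval, and the 10-month figures would be the error.

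**Conclusion.** The inconsistency is real and no section resolves it. Month 10 has the better support (the recall window in 9.1, the participation length in 10.2 and the label in 16.1), but the protocol does not make it definite. At month 10, the durability interval is understated by roughly 2-3 months. At month 7-8, the falls and emergency-visit recall includes 2-3 months before baseline. These sizes rest on the stated 1-2 month intervention, a start at or soon after baseline, and months counted from baseline.

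Separately, the comparison named for question 5 measures change since month 4 and does not say whether an effect exists at the end.

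The fault is one of timing, labelling and the choice of contrast for a follow-up question. It leaves the sample size and the month-2 and month-4 comparisons untouched. It should be corrected, because the wording decides both when the call is made and what the durability result is taken to mean.

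**What to change.** Set one date for the final assessment, counted from baseline in both arms.

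- **Preferred: month 10.** It fits the 9.1 recall window, 10.2 and 16.1. Describe it in 1.2, Background 2.1, 3.1, 9.1 and 16.1 as about 8-9 months after the intervention, or six months after the 4-month follow-up. State that the recall of falls and emergency visits runs from baseline.
- **Alternative: month 8.** This keeps the six-month aim, since month 8 is 8 − 2 = 6 to 8 − 1 = 7 months after the intervention. Shorten the recall to the 8 months since baseline and amend the 10-month figures in 9.1, 10.2 and 16.1.

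Under either option, state in 16.1 that question 5 is answered by the between-group difference at the final assessment. Report the planned month-4 versus final comparison beside it as change since follow-up. A contrast from the month-2 posttest to the final assessment is optional.

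The cost is wording in a handful of sections and one named contrast on data already planned, with no extra visits, staff or participants. Keeping month 10 gives up the claim to a result at exactly six months after the intervention.

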When the detailed challenges were documented, the OTGS may recommend some solutions, if she has, such as educating the process of Alzheimer's disease and suggesting an assistive device, good grip utensils.

At the end of the interview, the participant will be paid \$20.00.

The UB geriatric team including OTs, a gerontologist, and OTGS will brainstorm to develop solutions to identified problems. Within a week, these solutions will be presented to the participant and the OTGS and the participants will decide final solutions that the participant will perform. We use a caregiver-centered approach to facilitate their motivation to continue their care. The proposed approach will emphasize working collaboratively with caregivers to identify challenges and individualized strategies for each caregiver to solve specific problems. This is a different approach from the traditional therapist-client relationship, in which therapeutic prescriptions are made and provided by OTs to their clients.

Agreed-upon solutions will be reported to the PACE, especially if suggestions involve CRs. If assistive devices are needed, the PACE will provide them along with proper training for use.

Example interventions include: (a) didactic education about diseases; (b) the use of errorless techniques to improve assistance for CR's ADL,

IADL, and communication tasks; (c) the use of incentives (e.g., providing a favorite scented shampoo, going for an ice cream after going to a hair stylist, having a snack or short game to prevent going to bed right after dinner); (d) use of the Buffalo Functional Exercise for strengthening (a home-based exercise developed for PACE by the PI and shown to be effective in preventing falls, as reported by the NY Dept. of Health; attached); (e) use of a schedule/calendar on a computer, cell phone and/or blackboard in CR's home to coordinate caregiving tasks for family members; (f) suggesting more frequent PACE daycare visits or use of a nearby PACE-recommended daycare center; and (g) home safety suggestions using the Home Safety Self-Assessment Tool (HSSAT) to prevent falls in CR's home environment. We expect that more customized solutions will arise from this project.

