19.0 Risks to Subjects

19.1 List the reasonably foreseeable risks, discomforts, hazards, or inconveniences to the subjects related to their participation in the research. Consider physical, psychological, social, legal, and economic risks. Include a description of the probability, magnitude, duration, and reversibility of the risks.

NOTE: Breach of confidentiality is always a risk for identifiable subject data.

Response:

While being asked about depression in the past week, participants may be upset. We consider this as a minimal risk. But if the data shows that the participant is depressive, we will take an immediate action described above.

While a caregiver is helping the care recipient's activities of daily living using a new technique that are learned from us, such as a new transfer method, they may make a mistake and fall and have an injury. However, prevention of falls is one our study purpose.

19.2 Describe procedures performed to lessen the probability or magnitude of risks, including procedures being performed to monitor subjects for safety.

Response:

If a participant appears to be upset, the interviewer (OTGS) will ask if he/she would like to continue the interview or not. If they wants to continue after

a little rest, the interview will be resumed. If not, an interview at another time will be asked to complete the interview and make an appointment. In addition, if he/she scores 15 or more in the total CES-D, it will be informed to the participant and the PACE. The PACE may inform the PI about withdrawal of the participant from this study. We do not know the PACE criteria for the decision, but we will follow the PACE's decision.

Physical injury may occur while assisting care recipients' activities of daily living, but the purpose of the study is to prevent that. Any newly learned methods may cause discomfort or a fall, if the method is applied in a wrong way. Therefore, OTGS will show an intervention and caregivers will practice it until they become comfortable. An illustrated instruction will be provided for caregivers, if necessary or requested.

19.3 If applicable, indicate which procedures may have risks to the subjects that are currently unforeseeable.

Response:

Assisting transfer from a bed to a standing position and getting up from a couch.

If applicable, indicate which research procedures may have risks to an embryo or fetus should the subject be or become pregnant.

Response: N/A

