23.0 Consent Process

23.1 Indicate whether you will be obtaining consent.

NOTE: This does not refer to consent documentation, but rather whether you will be obtaining permission from subjects to participate in a research study. Consent documentation is addressed in Section 27.0.

Yes (If yes, Provide responses to each question in this Section)
 No (If no, Skip to Section 27.0)

23.2 Describe where the consent process will take place. Include steps to maximize subjects' privacy.

Response:

The consent process will take place either caregiver (participant)'s home or the care recipient home; therefore, the participant has a total control to secure his/her privacy.

23.3 Describe how you will ensure that subjects are provided with a sufficient period of time to consider taking part in the research study.

NOTE: It is always a requirement that a prospective subject is given sufficient time to have their questions answered and consider their participation. See "SOP: Informed Consent Process for Research (HRP-090)" Sections 5.5 and 5.6.

Response:

We will provide three opportunities for individuals to decide their participation in the study. First through an invitation letter, the second is the PI's initial phone call, and the third is a face-to-face conversation with an OTGS. At the last step, the consent form will be provided and they will be asked to read each section and have questions. All OTGS will have been trained to answer questions. During this consenting process, we will give sufficient time for participants to understand the study and ask questions. After they understood the study, they will be asked to sign the consent form.

23.4 Describe any process to ensure ongoing consent, defined as a subject's willingness to continue participation for the duration of the research study.

Response:

After obtaining written consent for the initial interview, in the beginning of 2nd and 3rd interview, participants will be asked their willingness to be in the study or not. In addition, this study will involve phone contacts with participants to find whether solutions are working and make a next appointment. At that time, if we suspect unwillingness to continue to be in the study, we will ask their wish to withdraw from the study. This will be followed by the PI's contact with them for confirmation.

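### The ratings planned for research question 2 have no comparator and no level for worsening, so they show perceived helpfulness, not which solutions were effective

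*Combined protocol and SAP*

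**What the plan says.** Section 1.2 of the combined protocol and SAP lists as its second research question: "Which solutions were accepted and effective". Section 3.1 describes a qualitative part, intended among other things "to document solutions and their implementation process", and a separate randomised part in which "a control group will receive usual support".

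For the research questions, section 16.1 states that "we will list all challenges for both groups and solutions for the treatment group". It then gives the only rule on whether solutions worked: "The effectiveness of solutions will be evaluated using a Likert Scale (from very effective to not effective at all) and percentages will be reported". It names no rater, time point or cut-off for calling a solution effective, and it states no analysis of acceptance.

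Three other places bear on how these ratings would be read.

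- **Section 9.1:** the team's solutions are presented to the caregiver, after which "the OTGS and the participants will decide final solutions that the participant will perform".
- **Section 23.4:** "this study will involve phone contacts with participants to find whether solutions are working". This suggests that the caregiver is the rater.
- **Section 19.1:** on caregivers who use a newly taught technique, "they may make a mistake and fall and have an injury". Section 19.2 adds that a wrongly applied new method may cause discomfort or a fall.

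**The concern.** The question uses the word effective, and section 16.1 uses the word effectiveness, but the planned data are ratings from one arm. Two things are lost.

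First, a challenge may ease, or a caregiver may adapt, without the solution having done anything. With no comparator, that improvement is credited to the solution.

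Second, the scale as described runs from strong benefit down to no benefit. A caregiver for whom a solution made matters worse has no stated level to choose and would presumably choose the lowest one, together with those for whom nothing changed. The protocol itself regards harm from taught methods as foreseeable.

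At stake is what may be concluded about single solutions. Section 9.6 says that aggregated data, including problems and solutions, will be shared with the PACE. It does not say that the ratings will be part of this. If they are, a label of effective would claim more than the data support, and a solution that did harm would look merely unhelpful.

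**Working it through.** **Plan's own figure.** The documents give no figure for research question 2. The stated 30 per group belongs to the two hypotheses and reproduces with a one-sided test: 2 × (1.645 + 0.842)² / 0.65² = 29.3, rounded up to 30 (29.97, also 30, with the t distribution). It does not bear on this point. I use 30 below only as a number of treated caregivers.

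**Step 1: comparator.** Let p1 be the share of treated caregivers who rate a solution effective, and p0 the share who would have done so had the solution done nothing. The quantity of interest is p1 − p0. Section 16.1 yields p1 only. Suppose 18 of 30 caregivers rate a solution effective (60%, Wilson 95% interval 42% to 75%). This fits p0 = 60% with an effect of 0. It fits p0 = 20% with an effect of 40 percentage points equally well. Nothing planned separates the two.

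**Step 2: can a false-positive rate be given?** The documents contain neither p0 nor a cut-off. As an illustration, take one rating from each of 30 caregivers, a solution that does nothing, and an assumed cut-off of at least half (15 or more) rating it effective:

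| Assumed p0 | Expected count of 30 | P(15 or more) |
|---|---|---|
| 20% | 6 | 0.0002 |
| 40% | 12 | 0.18 |
| 60% | 18 | 0.90 |

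The answer runs from almost never to nearly always, depending on an unknown input.

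A second route assumes that a caregiver rates a solution effective whenever the challenge has eased. Then p0 = Φ(s), where s is the natural drift in SD of change: Φ(−0.2) = 0.42, Φ(0) = 0.50, Φ(0.3) = 0.62. The documents do not give s, not even its sign. Any answer of unchanged would lower these values. No rate can be derived either way.

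**Step 3: harm.** Let w be the share of caregivers for whom a solution made things worse and z the share for whom it did nothing, and assume that both groups choose the lowest level. The reported lowest-level percentage is then w + z. A reported 30% (9 of 30) fits w = 0% with z = 30%, w = 30% with z = 0%, and every split between. This needs no assumption about size, only that the scale has no level below the stated lowest one.

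**Step 4: acceptance.** Under section 9.1, solutions are first presented and the final ones are then agreed. If all presented solutions are listed, acceptance can vary. If only the final ones are listed, every listed solution has been agreed to. Section 16.1 does not say which list is meant.

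**The case against.** The strongest reply is that question 2 is descriptive. Section 1.2 sets research questions beside two hypotheses, and section 16.1 gives this question a list and percentages with no test or decision rule. Causal claims rest on the between-group analyses of burden, depression, positive aspects of caregiving and self-efficacy, together with community living, falls and emergency visits. This stands, and it limits the severity. It does not justify the label: a descriptive percentage of favourable ratings is perceived helpfulness.

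A second reply is that controls receive usual support and have no study solutions to rate, and that solutions are individualised. This also stands. A reader might infer that the randomised design could have tested single solutions and failed to. The documents do not support that. Comparing change in listed challenges between the arms would be one more outcome of the whole programme.

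Third, harm has other routes to notice: the one-month follow-up contact, the phone contacts, the notes on implementation, the CES-D checks, and the comparison of care recipients' falls and emergency visits. So a reader should not infer that the trial is blind to harm. None of these, however, is tied by a stated rule to a single solution.

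Finally, the assessment form is attached to the submission but is not among the documents reviewed. It may contain further levels or free text. If it has a level for worsening, section 16.1 should say so. The lack of a comparator would remain.

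**Conclusion.** The point holds at modest severity. As written, section 16.1 cannot show that any single solution caused an improvement, and its stated anchors cannot separate a solution that made things worse from one that did nothing. Both conclusions follow from the text and need no assumed number. They rest on two readings: that the caregiver is the rater, inferred from section 23.4, and that the scale has no level outside its two stated ends.

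The two hypotheses, the primary endpoint and the sample size are unaffected.

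Two stronger statements should not be made. One is that at least half of useless solutions would be rated effective. It requires ratings driven by change in the challenge, no unchanged answers, symmetric change, and drift that is zero or favourable, and the documents give none of these. The other is that acceptance is true by construction. That depends on which solutions are listed, which the plan leaves open.

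**What to change.** In section 16.1 and the assessment form:

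1. Add a level for 'made things worse' and an explicit level for 'no change', and state who rates and when.
2. Report the percentages as perceived helpfulness, not effectiveness, and reserve claims of effectiveness for the randomised between-group comparisons of the whole programme. Reword research question 2 to match.
3. Report acceptance with all solutions presented to the caregiver as the denominator, split into declined, agreed but not tried, and tried.

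Optionally, rate the change in each listed challenge in both arms at interviews already planned. This would be an additional programme-level outcome, not evidence on single solutions. Because the number of challenges per caregiver is open, it would lengthen interviews by an unknown amount, so it is not needed for the repair.

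The three numbered changes cost an extra response level, slightly more record keeping and a more modest claim for individual solutions. They need no extra visits or participants.
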